6.4.5.2 Reporting

All AEs occurring during this clinical trial after the subject has received the first study product (i.e., at the Product Trial) must be recorded on the CRF, including the date and time of onset, action taken, outcome (resolved, improved, unchanged, worse, fatal, or unknown/lost to follow-up), duration, relationship to product administration, and severity for each event. AEs will be listed.

Events captured between Screening and the first study product use will be documented as baseline signs and symptoms.

The Investigator will review each event and assess its relationship to product administration as unrelated, unlikely, possibly, probably, or likely.

In addition, each sign or symptom reported will be graded on a 3-point severity scale using mild, moderate, or severe.

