1.2 Pulze HT Previous Clinical Experience

No clinical studies have been conducted for the Pulze HT products. Pulze was commercially available following a city pilot launch in Fukuoka, Japan, in May 2019.

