6.2 Check-in and Confinement

Subjects will check in to the CRU on Day -1 at a time specified by the CRU. Check-in procedures will be performed as delineated in the Study Events Flow Chart ([Table 1](#)).

After check-in, subjects will complete one set of questionnaires for the purpose of familiarisation with subjective effects questions, appropriate use of the VAS, and use of the computerised tablet system. Data collected from the training session will not be used for any analysis.

The clinical team will explain how the HT products will be used. Subjects will have the opportunity to see the products/devices and packaging and will participate in a Product Trial where they will use the [REDACTED] device with the HT stick (flavour) of their choice. The HT stick flavour will be recorded; however, no assessments will be made. The purpose of the Product Trial is to familiarise subjects to the [REDACTED] device and HT stick prior to PK assessments. All products/devices used in the trial session will not be used in the clinical study but will be retained as demonstration samples for accountability purposes.

Subjects will have their personal belongings thoroughly checked during Check-in. All subjects will be required to shower and will receive clean articles of clothing prior to the start of each morning controlled product use (i.e., during the 12-hour abstinence) on Days 1, 2, 3 and 4.

Subjects will be confined from Check-in on Day -1 through completion of scheduled study events on Day 4.

A subject may be required to remain at the CRU for longer at the discretion of the Investigator or designee.

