12.4 Adverse Events

AE will be coded (to the preferred term) with Medical Dictionary for Regulatory Activities (MedDRA®) Version 24.1.

A study product use-emergent adverse event (PUEAE) is defined as an AE that is starting or worsening at the time of or after study product administration. Each PUEAE will be attributed to a product based on the onset date and time of the AE. AEs occurring prior to the first product use episode on Day 1 but after the product trial has started on Day -1 will be attributed to the product trial.

All events captured in the database will be listed in by-subject data listings. However, only PUEAEs will be summarised.

Frequencies of subjects with PUEAEs, regardless of relationship to study product will be summarised by study product and sorted by system organ class and preferred term. The number of PUEAEs will be tabulated in a similar manner. Tables which summarize the number of PUEAEs and number of subjects with PUEAEs by severity and relationship to study product will also be included.

Subjects only enrolled in the product trial and dropped prior to randomisation will be summarised separately.

Serious adverse events (SAEs), if present, will also be listed. Applicable narratives will be included in the CSR.

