12.5 Clinical Laboratory Tests (Serum Chemistry, Hematology, Urinalysis)

Clinical laboratory evaluations will be performed at Screening, Day -1, and at End-of-Study (EOS) or upon early termination.

Out-of-normal range flags will be recorded as follows: high (H) and low (L) for numerical results and did-not-match (*) for categorical results. Out-of-range values and corresponding recheck results will be listed.

Imperial Brands PLC
Project No. NER01/0004
Celerion Project No. CA35183

For all numeric laboratory values, descriptive statistics will be presented for each laboratory test by assessment time point except for screening. Change from baseline will be summarised in a similar manner. Baseline is defined as the result closest and prior to the first product use on Day 1 which may include unscheduled or recheck results. This will typically be the result collected on Day -1. Post-product-use unscheduled events or rechecks will not be included in summaries. Similarly early termination results will not be included in summaries.

For each laboratory test, a shift table will be developed to compare the frequency of the results at baseline (above normal, normal, or below normal) with the respective post product use results. For urinalysis tests, the categories are normal and outside normal

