12.7 Electrocardiogram

Electrocardiogram will be performed at Screening, Day -1, and at EOS or upon early termination.

Descriptive statistics will be presented for each ECG parameter by assessment time point except for screening. Change from baseline will be summarised in a similar manner. Baseline is defined as the result closest and prior to the first product use on Day 1 which may include unscheduled or recheck results. This will typically be the result collected on Day -1. Post-product-use unscheduled events or rechecks will not be included in summaries. Similarly early termination results will not be included in summaries.

ECG data will be listed by subject and assessment timepoint. QTcF values that are > 450 msec and increase from baseline > 30 msec will be flagged in the data listing.

Imperial Brands PLC
Project No. NER01/0004
Celerion Project No. CA35183

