Table 14.3.4.1 Out-of-Range Values and Recheck Results - Serum Chemistry

Subject Number	Age/ Sex	Study Period	Day	Hour	Date	Time	Parameter1 <Range> (Unit)	Parameter2 <Range> (Unit)	Pa
X	XX/X	Screen	.	.	DDMMYYYY	HH:MM:SS	XX H		
			1	-X	DDMMYYYY	HH:MM:SS	XX L		
				-XX.XX				XX L	

F = Female, M = Male

H = Above reference range, L = Below reference range

Programmer Notes: Replace Parameter1, 2 etc. with actual lab tests in the study. Sort unscheduled as termination chronologically with other scheduled assessments and rechecks. Recheck should be sorted time point the recheck is for. Unscheduled and Early Termination records should only be included if results

Program: /CAXXXX/sas_prg/stsas/tab_PROGRAMNAME.sas DDMMYYYY HH:MM

Statistical Analysis Plan, 13 January 2022

Imperial Brands PLC
 Project No. NER01/0004
 Celerion Project No. CA35183

Tables 14.3.5.3 (hematology) and 14.3.5.5, (urinalysis) will resemble 14.3.5.1.

Table 14.3.5.1 Clinical Laboratory and Change From Baseline Summary - Serum Chemistry (Safety P

Laboratory Test (units)	Reference Range	Time Point	Statistic	Value	Change From B
Testname (unit)	< - >	Day -1	n	X	
			Mean	XX.XX	
			SD	X.XXX	
			Minimum	XX.X	
			Median	XX.XX	
			Maximum	XX.X	
		End of Study	n	X	X
			Mean	X.X	X.X
			SD	X.XX	X.XX
			Minimum	XX	XX
			Median	X.X	X.X
			Maximum	XX	XX

= Lowest of the lower ranges and highest of the higher ranges are used. Refer to Appendix 16.1.10. breakdown.

Baseline is the last measurement prior to Day 1 product use in the morning.

* Above Reference Range, ^ Below Reference Range

Programmer note: Treatment means at specific time points will be flagged (with a *) if they are above normal range. This only applies to the clinical laboratory treatment results (i.e., not the change for other endpoints).

Program: /CAXXXXX/ECR/sas_prg/stsas/tab programname.sas DDMMYYYY HH:MM

Statistical Analysis Plan, 13 January 2022

Imperial Brands PLC
 Project No. NER01/0004
 Celerion Project No. CA35183

Tables 14.3.5.4 (hematology), and 14.3.5.6 (urinalysis) will resemble 14.3.5.2

P
 Table 14.3.5.2 Clinical Laboratory Shift From Baseline - Serum Chemistry (Safety Population)

Laboratory Test (units)	Time Point	Baseline L			Baseline N			Baseline H		
		Post-use			Post-use			Post-use		
		L	N	H	L	N	H	L	N	H
Testname (unit)	End of Study	X	XX	X	X	XX	X	X	XX	X
Testname (unit)	End of Study	X	XX	X	X	XX	X	X	XX	X
Testname (unit)	End of Study	X	XX	X	X	XX	X	X	XX	X

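### Laboratory and ECG baselines can fall after the Day -1 Product Trial stick, and Product Trial adverse events are not shown by stick

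*Protocol*

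**What the plan says.** On Day -1 each subject uses one heated-tobacco stick of a flavour they choose. Protocol 6.2 adds: "The HT stick flavour will be recorded; however, no assessments will be made". Protocol 6.4.5.2 treats that stick as the first study product, since AEs "after the subject has received the first study product (i.e., at the Product Trial) must be recorded on the CRF". Only what comes before it is baseline: "Events captured between Screening and the first study product use will be documented as baseline signs and symptoms".

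For AEs the SAP keeps the same clock. SAP 12.4 says that AEs before the first Day 1 use "but after the product trial has started on Day -1 will be attributed to the product trial". Tables 14.3.1.1 to 14.3.1.4 give them a Product Trial column or row, and footnotes remove them from Overall.

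For laboratory tests the SAP uses a different clock. SAP 12.5 states: "Baseline is defined as the result closest and prior to the first product use on Day 1 which may include unscheduled or recheck results". SAP 12.7 has the same rule for ECGs. Both sections expect the Day -1 result to be the usual baseline. The table footnotes in SAP 15.2 repeat the rule: "Baseline is the last measurement prior to Day 1 product use in the morning". SAP 12.7 also says: "QTcF values that are > 450 msec and increase from baseline > 30 msec will be flagged in the data listing".

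SAP 12.6 expects the vital-sign baseline to be the Day 1 pre-use reading.

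**The concern.** One exposure is dated in two ways. A reaction to the trial stick counts as product-use-emergent in the AE tables. An ECG or blood sample taken because of that reaction would count as before product use in the ECG and laboratory tables, and it would displace the clean earlier value as the reference.

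The second part is about display. Secondary objective 4 is the tolerability and safety of each product, and Protocol 1.2 reports: "No clinical studies have been conducted for the Pulze HT products". The trial stick is each subject's first heated-tobacco use in the study, yet no AE table shows which stick was involved.

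**Working it through.** Neither document gives a figure on this point, so there is nothing to reproduce. The check sets the texts side by side and adds a small calculation for scale.

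**Step 1. Which use starts the clock**

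| Data | Source | First use | A finding between the stick and Day 1 use |
|---|---|---|---|
| AEs | Protocol 6.4.5.2 and 7.3.5; SAP 12.4 | Day -1 stick | Post-use, shown as Product Trial |
| Laboratory | SAP 12.5; Tables 14.3.5.1 to 14.3.5.6 | Day 1 morning | Becomes baseline |
| ECG | SAP 12.7; Table 14.3.5.8 | Day 1 morning | Becomes baseline |
| Vital signs | SAP 12.6; Table 14.3.5.7 | Day 1 morning | Day 1 pre-use reading is the usual baseline |

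SAP 12.5 and 12.7 also keep unscheduled and recheck results taken after product use out of the summaries. Dated from the stick, the extra result would be left out. Dated from Day 1, it becomes the reference value.

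**Step 2. How such a result could arise**

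Protocol 3.1 places the Product Trial after eligibility confirmation, so scheduled Day -1 tests should normally be done by then, although no text fixes the order for every test. Protocol 6.4.4 allows extra safety assessments at the Investigator's discretion, and 6.4.5.1 allows tests to document that an event has resolved. A reaction to the stick is one route to an extra test that evening.

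**Step 3. Effect on the change from baseline**

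Let B0 be the pre-stick value, B1 the value between the stick and Day 1 use, and E the end-of-study value.

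- Change from the pre-stick value: E - B0
- Change under the SAP rule: E - B1
- Difference (SAP minus pre-stick): B0 - B1

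If B1 is above B0, the SAP understates a rise. If B1 is below B0, it overstates one. If k of 24 subjects have such a result and their mean of B1 - B0 is d, the tabulated mean change moves by -k × d / 24, which is zero when k = 0. The documents give neither k nor d, and I assume no values.

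A laboratory shift category changes only if B0 and B1 lie on different sides of a reference limit. For QTcF, the 450 msec condition does not use the baseline; only the 30 msec change does. SAP 12.7 joins the two conditions, while the listing shell in Appendix 16.2.8.7 gives each its own symbol. Read jointly, the baseline matters only for subjects already above 450 msec. Read separately, it can matter for any subject.

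**Step 4. Scale of the AE pooling**

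With 24 subjects and one trial stick each, an even split would give 24 / 3 = 8 subjects per stick; free choice will make it uneven. For an assumed proportion p of subjects with an AE after the trial stick, the expected number is 24p, and the chance of at least one is 1 - (1 - p)^24.

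| Assumed p | Expected subjects | Chance of at least one |
|---|---|---|
| 2% | 0.5 | 38% |
| 5% | 1.2 | 71% |
| 10% | 2.4 | 92% |
| 20% | 4.8 | 99.5% |

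The documents give no such rate. Unless it is very low, the Product Trial column will probably have entries, but few for any one stick.

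**The case against.** The strongest reply is that little goes wrong in practice.

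- **The baseline route is uncommon.** The stick follows eligibility confirmation, no assessments are planned around it, and the SAP expects the Day -1 result as baseline. Eligibility is confirmed again on Day 1, so a subject with a clinically significant abnormality may never be randomised. This stands and limits the size of the point, but it does not remove a rule that expressly admits the later result.
- **Rechecks can regress towards normal.** A reader might infer that the error always hides harm. Step 3 shows that it can run either way, and for some parameters harm is a fall. This stands in full.
- **Laboratory and ECG data say nothing by product.** The one scheduled post-use result comes at end of study, after all four products, and the tables have no product columns. This also stands: the baseline rule does not damage a comparison between products.
- **No baseline is free of product use.** Subjects smoke their own brand, which is Product D. True, but exclusion criterion 23 bars other nicotine products for 14 days before Check-in, so a pre-stick value should be free of heated tobacco.
- **A self-chosen, unrandomised stick belongs outside the A to C columns.** Agreed. A separate breakdown by stick respects that.

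**Conclusion.** The point holds and is minor. The SAP dates first use from the Day -1 stick for AEs and from Day 1 for laboratory and ECG baselines. The second rule can put a post-exposure value in the baseline position. It affects only subjects with a laboratory or ECG result between the stick and Day 1 use; that number is unknown and may be zero. The direction of any distortion is not fixed.

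The AE part does not depend on that condition: any Product Trial AE is pooled across the three sticks and left out of Overall. A reader might infer that these AEs become baseline or disappear. They do not. Both documents treat them as post-use events, and the SAP tabulates them with severity and relationship and lists them by subject. What is missing is the breakdown by stick.

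Safety is a secondary, descriptive objective, and the primary Cmax and AUCt analysis is unaffected.

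**What to change.** 1. In SAP 12.5 and 12.7, and in the footnotes of Tables 14.3.5.1 to 14.3.5.6 and 14.3.5.8, define baseline as the last result before the Product Trial stick on Day -1. Show any laboratory or ECG result between that stick and Day 1 use as a Product Trial post-use value.
2. In SAP 12.6, state that the Day 1 pre-use vital-sign baseline is deliberate because it matches the pre-use timing on Days 2 to 4. Protocol 6.4.4.4 places these readings within 2 hours before morning use, and subjects abstain for at least 12 hours, so the Day 1 reading comes at least about 12 - 2 = 10 hours after the stick.
3. In Tables 14.3.1.1 to 14.3.1.4, break Product Trial AEs down by the recorded stick in descriptive sub-columns or rows, kept apart from the randomised periods. The record must distinguish Intense from Regular American Blend; confirm that the CRF does so.

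The cost is SAP wording, footnotes and a few sub-columns or rows. There are two small downsides. A recheck drawn after the stick can no longer serve as baseline. The counts per stick will be small and self-selected, so they support description only.

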6.4.5.3 Serious Adverse Events

A serious adverse event (SAE) is any untoward medical occurrence that (WHO and ICH definitions):

- results in death
- is life-threatening

- results in permanently disabling or incapacitating
- requires inpatient hospitalisation
- prolongs inpatient hospitalisation
- is a congenital anomaly / birth defect
- may jeopardise the subject or may require intervention to prevent one or more of the other outcomes listed above.

All SAEs, whether or not considered study-related, must be reported by telephone and by fax or e-mail to the Sponsor within 24 hours of the CRU's learning of the SAE or, at the latest, on the following workday. The Sponsor's representative to contact about this study is provided in the list of study contacts. The Investigator must also inform the EC, in compliance with GCP reporting guidelines, and the site monitor of any SAE.

6.4.5.4 Suspected Unexpected Serious Adverse Reactions

In accordance with the European Clinical Trial Directive (Directive 2001/20/EC), the Sponsor must ensure that the Ethics Committee, the appropriate Competent Authority, and the licensing authority are informed of all suspected "unexpected" serious adverse reactions (SUSARs) within 15 days of the event. All SUSARs leading to death, or which are life-threatening should be reported by the Sponsor to the ethics committee, the appropriate Competent Authority, and the licensing authority within 7 days of the event. The Sponsor should present all SUSARs to the appropriate Competent Authority once a year, or on request. Reporting of relevant events to ethics committee, the appropriate Competent Authority, and the licensing authority will be delegated by the Sponsor to the CRO (Celerion).

6.4.5.5 Pregnancy

A pregnancy occurring in a female study subject during the study will be documented in the clinical conduct study report to the EC. Pregnancy itself is not an AE. The Investigator or designee will discontinue the pregnant subject from the study and will advise her to seek prenatal care and counseling from her primary care provider. Advice given will be documented in the subject's source document.

The CRU staff will request the pregnant subject to notify the CRU of the outcome of the pregnancy (i.e., birth, loss, or termination). To help ensure this, the CRU staff will follow up with the subject until the end of pregnancy, if in compliance with the CRU's standard operating procedures (SOPs) and with the subject's consent. This request and the subject's response will be documented in the subject's source document.

6.4.5.6 Smoking Cessation Information

At Screening and prior to discharge from the study (or upon early termination), all subjects will be advised that to reduce the health effects of smoking, the best thing to do is to quit, and

will be encouraged to contact a qualified medical professional for advice on smoking cessation.

7. DATA ANALYSIS

Data will be handled and processed according to Celerion SOPs, which are written based on the principles of GCP. A brief description of the statistical analysis is included below, detailed methodology for all summary and statistical analyses of the data collected in this trial will be documented in a statistical analysis plan (SAP) prepared by Celerion and agreed upon by the Sponsor. The SAP may modify the plans outlined in the protocol; however, any major modifications of the primary endpoints and/or their analysis will also be reflected in a protocol amendment. If deemed appropriate, additional statistical analyses other than those described in this section may be performed and included in the plan.

7.1 Sample Size Estimation

The sample size chosen for this study was selected without statistical considerations. It has been determined adequate to meet the study objectives.

7.2 Analysis Populations

7.2.1 Safety Population

The Safety Population will include all subjects who have successfully completed eligibility requirements after checking in to the CRU and used at least one study product.

7.2.2 Outcomes Population

The Outcomes Population is a subset of the safety population and will consist of subjects who used a study product and have evaluable PK, subjective effects, or topography data. This population will be used in the summary and analysis of PK, subjective effects, topography, and product use, and all available data will be included in the summary tables to the extent possible.

7.3 Data Analysis, Summarisation, and Statistical Methods

SAS software (version 9.4 or higher, Cary, North Carolina) will be used for all data presentation and summarisation including summary tables, graphs, and data listings. In general, all data will be listed by subject and time point and summarised by study product, time point, product use session (as applicable), and sex using descriptive statistics appropriate for the endpoint. Figures will be used to display the data graphically.

Missing data will not be imputed. Where individual data points are missing because of dropouts or other reasons, the data will be considered missing at random and summarised based on reduced denominators.

7.3.1 Nicotine Pharmacokinetic Analysis

Individual nicotine concentrations will be adjusted for baseline nicotine (“baseline-adjusted”) and all PK parameters will be calculated based on the adjusted concentrations. Baseline adjustment will be performed by subtraction of the pre-existing nicotine concentration from each nicotine concentration obtained after test product administration in that period/day for each subject using the following equation:

$$C_t = C_{t \text{ unadjusted}} - [C_0 \cdot e^{-K_{el} \cdot t_1}]$$

where C_t is the adjusted concentration at time t , $C_{t \text{ unadjusted}}$ is the observed concentration at time t , C_0 is the pre-product use concentration (-5 minutes), $K_{el} = \frac{\ln(2)}{t_{1/2}}$, $t_{1/2}$ is 2 hours (average nicotine half-life), t is the actual sampling time since product administration, and t_1 is the actual sampling time since the time of the pre-product use sample. Any resulting negative concentration values following the baseline adjustment will be set to 0.

Nicotine PK parameters will be determined from the adjusted individual subject plasma concentration-time profiles by applying a non-compartmental approach using appropriate validated PK software (e.g., Phoenix® WinNonlin® version 8.1 or higher).

For each morning product use session on Days 1, 2, 3 and 4, the following PK parameters will be calculated from the baseline-adjusted nicotine concentration-time data:

AUC_{0-90}	Area under the baseline-adjusted nicotine concentration-time curve from time 0 (defined as the start of the product use session) to the 90-minute time point as calculated by the linear trapezoidal method
AUC_{0-240}	Area under the baseline-adjusted nicotine concentration-time curve from time 0 (defined as the start of the product use session) to the 240-minute time point as calculated by the linear trapezoidal method
AUC_t	Area under the baseline-adjusted nicotine concentration-time curve from time 0 (defined as the start of the product use session) to time t .
AUC_{inf}	Area under the baseline-adjusted nicotine concentration-time curve from time 0 (defined as the start of the product use session) extrapolated to infinity (represents the total nicotine exposure across time).
C_{max}	Maximum baseline-adjusted plasma concentration.
C_{last}	Plasma baseline-adjusted nicotine concentration at last time point measured
T_{max}	Time to reach the maximum baseline-adjusted plasma concentration. If the maximum value occurs at more than one time point, T_{max} is defined as the first time point with this value.
$T_{1/2}$	Terminal elimination half-life.

Plasma concentrations below the limit of quantitation will be set to one-half of the lower limit of quantitation for the calculation of descriptive statistics of unadjusted plasma nicotine concentrations and for the calculation of baseline-adjusted nicotine concentrations.

Nicotine concentrations and PK parameters will be listed by subject and summarised by study product, by sex and overall using descriptive statistics.

